## List of Abbreviations

Abbreviation	Definition
AE	Adverse Event
ATC	Anatomical Therapeutic Chemical
BSCVA	Best Spectacle Corrected Visual Acuity
CRF	Case Report Form
ECD	Endothelial Cell Density
ETDRS	Early Treatment of Diabetic Retinopathy Study
IOP	Intraocular Pressure
LogMAR	Logarithm of the Minimum Angle of Resolution
MedDRA	Medical Dictionary for Regulatory Activities
MD	Mean Deviation
mmHg	Millimeters of Mercury
OAG	Open-Angle Glaucoma
OHT	Ocular Hypertension
PE	Post-Exchange
PT	Preferred Term
SAE	Serious Adverse Event
SAP	Statistical Analysis Plan
SOC	System Organ Class
TEAE	Treatment Emergent Adverse Event
VA	Visual Acuity
VF	Visual Field
WHO	World Health Organization

## Version History

This Statistical Analysis Plan (SAP) for IDOS-106-EXCH is based on the protocol dated 24AUG2020.

## 1. Introduction

This statistical analysis plan (SAP) describes the statistical methods to analyze all safety data from protocol IDOS-106-EXCH. Any changes to this plan will be reflected as amendments before the database lock and/or documented in the clinical study report. One database lock will occur after all subjects have completed the Month 12 Post-Exchange (PE) visit or have exited the study prior to that time.

Specifications of tables, figures, and data listings are provided in another document.

## 2. Objectives and Study Design

## 2.1. Objectives

The study objective is to evaluate the safety of the surgical exchange procedure of the Travoprost Intraocular Implant in subjects with a previously implanted Travoprost Intraocular Implant.

[figure not shown]
## 2.2. Endpoints

## Safety Endpoints:

- Intraoperative adverse events
- Postoperative adverse events
- Corrected visual acuity (logMAR score using ETDRS chart)
- Slit-lamp biomicroscopy findings
- Gonioscopy findings
- Specular microscopy findings
- Intraocular Pressure
- Ophthalmoscopy findings
- Visual field evaluation

### 2.3. Study Design

The study consists of eight visits: Visit 1 (Screening), Visit 2 (Operative Exchange Day 0), Visit 3 (Day 1 Post-Exchange), Visit 4 (Day 10 Post-Exchange), Visit 5 (Week 4 Post-Exchange), Visit 6 (Month 3 Post-Exchange), Visit 7 (Month 6 Post-Exchange), and Visit 8 (Month 12 Post-Exchange). Subjects will exit the study at the conclusion of the Month 12 Post-Exchange visit.

**2.4. Schedule of Visits and Measurements**

## 2.5. Sample Size Determination

### 3. Analysis Sets

For the purposes of analysis, the following analysis set is defined:

Analysis Set	Description
Safety	All subjects who undergo the exchange procedure.

The safety analysis set will be used for all data tabulations and listings.

## 4. General Statistical Considerations

Demographic and safety data collected on the case report forms (CRFs) will be displayed in tabulations and data listings. Only data from scheduled visits will be used in tabulations unless otherwise specified. No formal statistical testing will be performed. All data summaries and statistical analyses will be performed using SAS® software, Version 9.4 or higher.

Continuous data will be summarized using the number of observations, mean, standard deviation, median, minimum, and maximum. Continuous data may also be dichotomized, or otherwise split, into clinically meaningful categories and may be further analyzed as categorical data as specified in the individual endpoints.

Categorical data will be summarized using frequency counts and percentages. Unless otherwise stated, subjects with missing visit data will be omitted from both the numerator and denominator of such calculations.

### 4.1. Definition of Variables

#### 4.1.1. Baseline Measure

The baseline measure is defined as the last non-missing measure prior to the initiation of the investigational product within this study (i.e., second implant at the operative exchange visit).

#### 4.1.2. Change and Percent Change from Baseline

The change from baseline and the percent change from baseline values are calculated as

- Change from baseline value = follow-up visit value – baseline value.
- Percent Change from baseline value =  $(\text{change from baseline value} / \text{baseline value}) * 100$ .

#### 4.1.3. Study Days

[figure not shown]
The number of study days is defined relative to the Operative Exchange visit, starting with the Operative visit as study day 1. For each date following the Operative visit, the study day value increases by 1. For each date prior to the Operative visit, the study day value decreases by 1, with the date preceding the Operative visit as study day -1. Note that the operative visit is sometimes referred to as the Operative Exchange Day 0 visit in the protocol. In the statistical analysis plan and summaries, this visit will be considered day 1.

## 5. Demographic and Baseline Characteristic Analyses

### 5.1. Subject Disposition

The number and percentage of subjects who were screened, screened but not enrolled (i.e., screen failures), and enrolled will be provided. A subject is considered enrolled at the time the subject undergoes surgery. Reason(s) for screen failure will also be presented in a table and subject listing.

Subject disposition will be summarized for all enrolled subjects. The summary will include the number and percentage of subjects who completed the study and the number and percentage of subjects who exited early (with reasons for study exit) prior to the Month 12 PE examination. The reasons for early study exit include:

Subject disposition and exit status will also be listed by subject.

### 5.2. Protocol Deviations

Protocol deviations will be captured by the site and reviewed by a medical monitor during the study. Classification of major deviations will be decided by the study team prior to the database lock. A summary of protocol deviations will be tabulated for the safety analysis set. A listing of all protocol deviations will be provided.

### 5.3. Demographic and Baseline Characteristics

Subject demographics and baseline characteristics will be tabulated for the safety analysis set. Demographic variables include age, sex, race, and ethnicity. Age will be calculated for each subject by  $(\text{Informed Consent Date} - \text{Date of Birth}) \div 365.25$  and rounded down to the nearest integer.

The following baseline characteristics will be summarized for the study eye:

- Type of Disease (OAG or OHT) [REDACTED].)
- IOP (mmHg)
- Best Spectacle Corrected Visual Acuity (BSCVA) - LogMAR
- Visual Field Mean Deviation (dB)
- Vertical Cup-to-Disc Ratio
- Corneal Thickness ( $\mu\text{m}$ )

Demographic and baseline characteristic data will be listed.

#### **5.4. Medical and Surgical History**

All medical and surgical history will be coded to the Medical Dictionary for Regulatory Activities (MedDRA) nomenclature, [REDACTED]. Ocular and non-ocular medical and surgical history will be tabulated by System Organ Class (SOC) and preferred term (PT). The ocular history tabulation will present summaries for the study eye, non-study eye, and overall groups. Subjects with more than one medical history within a given SOC or PT will only be counted once within that SOC or PT. Ocular and non-ocular medical and surgical history will be listed by subject.

#### **5.5. Prior and Concomitant Medications**

Prior medications are defined as those medications taken within 30 days prior to the start of Screening with a stop date prior to study drug administration. Concomitant medications are defined as those medications taken (1) prior to study drug administration and continuing for any period of time following the first administration of study drug or (2) at any time following the first administration of study drug.

Medications will be coded using the World Health Organization (WHO) Drug Dictionary [REDACTED] and will be summarized to the anatomical therapeutic chemical (ATC) class and preferred name. Prior and concomitant ocular medications will be tabulated separately. The tabulations will present summaries for the study eye, non-study eye, and overall groups. Subjects will be counted only once under each ATC class or preferred name for which they have at least one medication. All prior and concomitant medications will be listed.

#### **5.6. Concurrent Ocular Procedures**

Concurrent ocular procedures are defined as any ocular procedures that occurred in the study eye on or after the date of the exchange surgery. Ocular procedures will be coded using the MedDRA nomenclature, [REDACTED]. Ocular procedures will be tabulated by SOC and PT. Subjects with more than one ocular procedure within a given SOC or PT will only be counted once within that SOC or PT. All concurrent ocular procedures will be listed.

## **6. Efficacy Analyses**

### **6.1. Primary Endpoint Efficacy Analysis**

There are no primary efficacy endpoints in this study.

### **6.2. Secondary Endpoint Efficacy Analysis**

There are no secondary efficacy endpoints in this study.

### **6.3. Exploratory Endpoint Efficacy Analysis**

There are no exploratory efficacy endpoints in this study.

## 7. Safety Analyses

All safety analyses will be based on the safety analysis set and will be described in more detail in the following sections.

### 7.1.1. Extent of Exposure

Summaries of the extent of exposure to study treatment, which include the number of participants exposed and descriptive statistics of the duration of exposure in study days, will be provided for the study. Extent of exposure to study treatment in days will be calculated as date of study exit – date of exchange surgery + 1. If the date of study exit is missing for a subject with early study exit, the date of the last recorded visit will be used for calculations. A listing of extent of exposure will be provided.

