The study objective is to evaluate the safety of the surgical exchange procedure of Travoprost Intraocular Implant in subjects with a previously implanted Travoprost Intraocular Implant.

STUDY TREATMENTS

Subjects will undergo an exchange of a Travoprost Intraocular Implant through a small temporal clear corneal incision.

Structure: Single arm

Number of Centers: Approximately 15 centers

Masking: Open-label

Method of Subject Assignment:

After Visit 1 (Screening), qualified subjects will be scheduled to undergo treatment with the G2TR-█ implant.

Randomization: No

Total Sample Size: Approximately [REDACTED] subjects

Statistical Rationale Provided: Please refer to Statistical Section, [Section 8](#)

STUDY OVERVIEW

Subjects will be assessed for inclusion/exclusion criteria at Visit 1 (Screening). At this visit, all subjects must meet all entry criteria. Subjects who meet criteria at Visit 1 (Screening) may be scheduled for Visit 2 (Operative Exchange Day 0) (on a separate day).

Visit Schedule:

This study will consist of 8 visits over approximately a 12 month period: Visit 1 (Screening), Visit 2 (Operative Exchange Day 0), Visit 3 (Day 1 Post-Exchange), Visit 4 (Day 10 Post-Exchange), Visit 5 (Week 4 Post-Exchange), Visit 6 (Month 3 Post-Exchange), Visit 7 (Month 6 Post-Exchange), and Visit 8 (Month 12 Post-Exchange).

Study Measures will be collected for the study eye only:

Safety

- Intra-operative adverse events
- Post-operative adverse events
- Corrected visual acuity (logMAR score using ETDRS chart)
- Slit-lamp biomicroscopy findings
- Gonioscopy findings
- Specular microscopy findings
- Intraocular Pressure
- Ophthalmoscopy findings
- Visual field evaluation

Other

- Operative and surgical assessments

Specified Plan for Data Analysis: Yes (refer to [Section 8](#))

Power and Sample Size: The sample size of [REDACTED] who undergo an exchange of a Travoprost Intraocular Implant was determined empirically. This sample size is considered adequate to support the objective of this study.

STUDY VARIABLES AND STATISTICAL ANALYSIS

Efficacy Variable

There is no efficacy variable in this study. Intraocular pressure is assessed for safety.

Safety Variables

Adverse events (intra-operative and post-operative [TEAEs]) in the study eye will be monitored and summarized.

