6.2.3.2 After 2nd Cycle Implantation

Subjects may be exited (discontinued) from the study in the event of a condition that may cause them harm if participation were to be continued. Subjects may also withdraw voluntarily.

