6.3.4.5 Visit 6 (Month 3 Post-Exchange, 91 days \pm 14)

6.3.4.6 Visit 7 (Month 6 Post-Exchange, 182 days \pm 30)

6.3.4.7 Visit 8 (Month 12 Post-Exchange, 365 days ± 30)

6.4 Concomitant Therapies

6.4.1 MEDICATIONS OR TREATMENTS

Therapy considered necessary for the subject's welfare that will not interfere with the evaluation of the study medication may be given at the discretion of the investigator.

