6.5 Post-Treatment Management of IOP and Rescue Medications

7 EXTENT OF EXPOSURE AND TREATMENT COMPLIANCE

All subjects will be implanted with a second Travoprost Intraocular Implant to exchange with the previously implanted first one that will be explanted. All subjects will be followed for the duration of the study.

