### 7.1.2. Adverse Events

Adverse events (AEs) will be coded to the MedDRA nomenclature, [REDACTED]. Treatment Emergent Adverse Events (TEAEs) are defined as AEs that occur after the initiation of the exchange surgery at Visit 2 (Operative Exchange Day 0).

A summary of the number and percentage of subjects with TEAEs will be provided for the safety analysis set. The summary will include study eye TEAEs, non-ocular or non-study eye TEAEs, treatment-related TEAEs, TEAEs by maximum severity, TEAEs resulting in study discontinuation, serious TEAEs, and deaths.

The number and percentage of subjects with TEAEs will be tabulated by SOC and PT for:

- Ocular TEAEs
- Non-ocular TEAEs
- Ocular TEAEs related to study treatment
- Non-ocular TEAEs related to study treatment
- Ocular TEAEs by maximum severity
- Non-ocular TEAEs by maximum severity
- Ocular serious TEAEs
- Non-ocular serious TEAEs

All tabulations of ocular TEAEs will contain summaries for the study eye, non-study eye, and overall groups.

All AEs will be presented in a listing by subject. Separate listings for intraoperative AEs, serious adverse events (SAEs) including deaths, AEs leading to early study exit, and AEs leading to removal of implant will also be presented.

Relationship to study treatment is defined as the possibility that the study treatment caused the event and is described in the study protocol. The relationship to study treatment categories utilized on the CRF are definitely unrelated, unlikely related, possibly related, probably related, and definitely related. For all tabulations, the categories of possibly related, probably related, and definitely related will be classified as related and only related AEs will be presented. AEs

[figure not shown]
with missing relationships are counted as related. Subjects experiencing more than one treatment related AE within a given SOC or PT will be counted once within that SOC or PT.

Severity is a measure of intensity and is graded on a 3-point scale as outlined in the study protocol. AEs will be rated as either mild, moderate, or severe. AEs with missing severities are counted as severe. For all tabulations, subjects experiencing more than one AE within a given SOC or PT will be counted once within that SOC or PT at the maximum severity.

[figure not shown]

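### The exposure formula in SAP 7.1.1 has no term for removal of the second implant, so a subject followed after removal is credited with exposure that did not occur (minor)

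*SAP*

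**What the plan says.** SAP 7.1.1 promises "descriptive statistics of the duration of exposure in study days" and a by-subject listing. The rule is "Extent of exposure to study treatment in days will be calculated as date of study exit" minus the exchange surgery date, plus 1. If the exit date of an early-exit subject is missing, the last recorded visit takes its place. The paragraph shows no redaction, and the derivation appendix in SAP 11 covers only visual acuity and IOP.

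Three other places bear on the point:

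- **What the treatment is.** The protocol synopsis states that "qualified subjects will be scheduled to undergo treatment with the" implant. Protocol 7, under its exposure heading, states: "All subjects will be implanted with a second Travoprost Intraocular Implant to exchange with the previously implanted first one". SAP 4.1.1 identifies the investigational product as the second implant.
- **Removal is foreseen.** SAP 7.1.2 states that separate listings of "AEs leading to early study exit, and AEs leading to removal of implant will also be presented".
- **Exit at removal is not required in the readable text.** Protocol 6.2.3.2 is permissive: "Subjects may be exited (discontinued) from the study in the event of a condition that may cause them harm". Protocol 7 adds: "All subjects will be followed for the duration of the study".

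**The concern.** The formula measures time in the study. That equals time with the implant only if the implant stays in place until exit, or if exit always coincides with removal. The plan names removal as a possible outcome and lists it apart from early exit. The listing must refer to the second implant: every first implant is removed by design, and Protocol 9 sends events before the procedure to medical history.

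In a safety study it is reasonable to keep observing an eye after its implant has been removed. For such a subject the stated rule gives a wrong value. The mean exposure would be too high, and the true minimum and spread would not be shown. The by-subject listing would give about a year of exposure for an eye that carried the implant for a shorter time, at odds with the removal listing in the same report.

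**Working it through.** The documents give no exposure figure to reproduce, so the check applies the stated rule and the corrected rule to the same hypothetical subjects.

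**Inputs from the documents**
- About 45 subjects (Protocol 6.1).
- Month 12 visit at 365 ± 30 days, so planned exit falls between day 335 and day 395 (Protocol 3 and 6.3.4.7).
- Exposure is summarized by mean, SD, median, minimum and maximum (SAP 4).

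**Assumptions**
- Removal at day 10, 91 or 182. The documents give no removal rate or timing.
- Exit day uniform over the 61 whole days from 335 to 395.
- No early exits; this is relaxed in step 5.
- Days are counted from the exchange as day 0, as in the protocol's visit windows.

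**1. One subject.** Stated rule: exit day + 1. Corrected rule: removal day + 1. With removal at day 91 and exit at day 365, these give 365 + 1 = 366 and 91 + 1 = 92, a difference of 274 days.

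**2. Reported distribution.** Mean = 365 + 1 = 366. Variance = (61² − 1)/12 = 310, so SD = 17.6.

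**3. One removal among 45, at day d.**
- Expected excess in the mean = (365 − d)/45.
- Range over that subject's exit day = (335 − d)/45 to (395 − d)/45.
- True SD = √[310 × 44/45 + (365 − d)²/45].

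| Removal day d | Excess in mean (days) | Range (days) | True mean | Relative excess | True SD | True minimum |
|---|---|---|---|---|---|---|
| 10 | 355/45 = 7.9 | 7.2–8.6 | 358.1 | 2.2% | 55.7 | 11 |
| 91 | 274/45 = 6.1 | 5.4–6.8 | 359.9 | 1.7% | 44.4 | 92 |
| 182 | 183/45 = 4.1 | 3.4–4.7 | 361.9 | 1.1% | 32.4 | 183 |

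For d = 91 the SD is √(303.1 + 75,076/45) = √(303.1 + 1,668.4) = 44.4. In a simulation of 100,000 replicates per case, the reported SD was 17.6 (95% range 15.1–19.9), the reported minimum averaged 336.9 (95% range 336–340), and the median moved by 0.7 day on average.

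**4. More removals, or a different N.** The excess in the mean scales with the number of removals.
- Two removals: 15.8 (day 10) to 8.1 (day 182) days.
- Three removals: 23.7 to 12.2 days.
- One removal with N = 40: 355/40 = 8.9 to 183/40 = 4.6 days.
- One removal with N = 50: 7.1 to 3.7 days.

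**5. If someone else exits early.** Suppose one unrelated subject exits at day 91 with the implant in place. The reported SD is then already about 44.4 and the reported minimum 92. If a second subject has a removal at day 91 and stays in follow-up, the true SD is √[310 × 43/45 + 274² × (2 × 43)/(45 × 44)] = √(296.2 + 3,260.9) = 59.6, and the true minimum is still 92. The SD contrast narrows to 44.4 against 59.6, and the minimum contrast disappears. The excess in the mean stays at 6.1 days.

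**The case against.** The strongest objection is that the error depends on what happens after removal, and the places most likely to settle that cannot be read: Protocol 6.5, the visit procedures, and the exit reasons in SAP 5.1. Separate listings do not prove that subjects stay after removal, because one event can lead to both. The statement in Protocol 7 about following all subjects is general and is already qualified by the withdrawal and loss-to-follow-up rules. This stands as a limit. The readable text permits continued follow-up but does not establish it.

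A second objection is that the study treatment is the exchange procedure. The synopsis describes it that way under its treatments heading, and the objective concerns the procedure. On that reading, surgery to exit is simply time observed. This does not hold for the summary at issue: a procedure completed in one day has no duration in days, and SAP 4.1.1 names the second implant as the investigational product.

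A third objection is that the harm is small, and this stands. There may be no removals. The contrasts in SD and minimum are largest when nobody exits early. Removals remain visible in the adverse event listing and among the concurrent ocular procedures of SAP 5.6. Adverse event results are counts and percentages of subjects, so nothing else uses exposure time.

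**Conclusion.** The concern holds as a minor, conditional correction. Applied as written, the rule gives a wrong exposure value for any subject whose second implant is removed and who remains in follow-up. The over-credit is 274 days in the worked case, and each such subject adds about 4 to 8 days to the mean for removals between day 182 and day 10. These figures rest on N = 45, exit within the Month 12 window and assumed removal days; the SD and minimum contrasts also rest on there being no early exits. The effect is confined to one descriptive table and one listing. If unseen text requires exit at removal, the formula is close to correct and lacks only the statement that makes it so. Confidence is medium for that reason.

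**What to change.** In SAP 7.1.1, define exposure as the earlier of the second-implant removal date and the study exit date, minus the exchange surgery date, plus 1. Keep the last-recorded-visit rule for a missing exit date. Add a row to the exposure table for surgery-to-exit, labelled as follow-up, so that both quantities are reported. If the protocol already requires exit at removal, add a clause to SAP 7.1.1 saying so instead.

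The cost is one sentence in the SAP, one table row, and confirmation that the CRF records the removal date. A later removal would fall under the concurrent ocular procedures of SAP 5.6. That definition turns on timing relative to the exchange, which suggests a date is collected, but the readable text does not confirm it. SAP 1 allows the change as an amendment before database lock or as documentation in the clinical study report.

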### 7.1.2. Adverse Events

Adverse events (AEs) will be coded to the MedDRA nomenclature, [REDACTED]. Treatment Emergent Adverse Events (TEAEs) are defined as AEs that occur after the initiation of the exchange surgery at Visit 2 (Operative Exchange Day 0).

A summary of the number and percentage of subjects with TEAEs will be provided for the safety analysis set. The summary will include study eye TEAEs, non-ocular or non-study eye TEAEs, treatment-related TEAEs, TEAEs by maximum severity, TEAEs resulting in study discontinuation, serious TEAEs, and deaths.

The number and percentage of subjects with TEAEs will be tabulated by SOC and PT for:

- Ocular TEAEs
- Non-ocular TEAEs
- Ocular TEAEs related to study treatment
- Non-ocular TEAEs related to study treatment
- Ocular TEAEs by maximum severity
- Non-ocular TEAEs by maximum severity
- Ocular serious TEAEs
- Non-ocular serious TEAEs

All tabulations of ocular TEAEs will contain summaries for the study eye, non-study eye, and overall groups.

All AEs will be presented in a listing by subject. Separate listings for intraoperative AEs, serious adverse events (SAEs) including deaths, AEs leading to early study exit, and AEs leading to removal of implant will also be presented.

Relationship to study treatment is defined as the possibility that the study treatment caused the event and is described in the study protocol. The relationship to study treatment categories utilized on the CRF are definitely unrelated, unlikely related, possibly related, probably related, and definitely related. For all tabulations, the categories of possibly related, probably related, and definitely related will be classified as related and only related AEs will be presented. AEs

[figure not shown]
with missing relationships are counted as related. Subjects experiencing more than one treatment related AE within a given SOC or PT will be counted once within that SOC or PT.

Severity is a measure of intensity and is graded on a 3-point scale as outlined in the study protocol. AEs will be rated as either mild, moderate, or severe. AEs with missing severities are counted as severe. For all tabulations, subjects experiencing more than one AE within a given SOC or PT will be counted once within that SOC or PT at the maximum severity.

[figure not shown]

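### SAP 7.1.2 applies a related-only rule to all adverse event tabulations, which contradicts the section's own list of tables; its scope needs to be stated

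*SAP*

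**What the plan says.** SAP 7.1.2 sets out the adverse event output in this order.

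- An overview: "A summary of the number and percentage of subjects with TEAEs will be provided for the safety analysis set". Its rows include study-eye events, treatment-related events, maximum severity, discontinuations, serious events and deaths.
- A list of eight tables, introduced by "The number and percentage of subjects with TEAEs will be tabulated by SOC and PT for". Two are limited by name to related events: "Ocular TEAEs related to study treatment" and "Non-ocular TEAEs related to study treatment". The other six are the ocular and non-ocular tables of all TEAEs, of TEAEs by maximum severity (for example "Ocular TEAEs by maximum severity") and of serious TEAEs. None of these six names a causality limit.
- Listings: one of all adverse events by subject, and separate ones for intraoperative events, serious events including deaths, events leading to early exit and events leading to implant removal.
- A paragraph on relationship. The CRF grades are "definitely unrelated, unlikely related, possibly related, probably related, and definitely related". The rule then follows: "For all tabulations, the categories of possibly related, probably related, and definitely related will be classified as related and only related AEs will be presented". Events "with missing relationships are counted as related".

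Protocol 8.5.1 plans separate summaries of intra-operative events and TEAEs, with no restriction by causality. SAP Section 10 declares no change from the protocol's planned analyses.

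**The concern.** The rule names its own scope, and that scope is every tabulation. Nothing else in the SAP narrows it. A programmer who follows it would remove from the overview, severity and serious-event tables each event that the investigator graded definitely unrelated or unlikely related.

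This matters more here than in most trials. Safety of the exchange procedure is the only objective, there is no efficacy endpoint and no formal testing, and the study is single-arm and open-label. The descriptive adverse event tables are therefore a main result, and the filter would rest on an unmasked investigator's causality call. The relationship definitions in protocol Section 9 are also worded around drug administration and the known response to the study medication, not around the surgery. An event caused by the procedure could be graded low on that scale and then drop out of the tables.

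**Working it through.** No numerical figure in the plan is involved. The check is to apply the rule under each reading to the output that SAP 7.1.2 promises.

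| Output in SAP 7.1.2 | Rule applied to all tabulations | Rule limited to related-event tabulations |
|---|---|---|
| Overview | every row related-only; the treatment-related row equals the any-TEAE count | only the treatment-related row restricted |
| Ocular and non-ocular TEAEs (2 tables) | related-only | regardless of relationship |
| Related TEAEs, ocular and non-ocular (2) | related-only | related-only |
| By maximum severity, ocular and non-ocular (2) | related-only | regardless of relationship |
| Serious, ocular and non-ocular (2) | related-only | regardless of relationship |

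**Count of tables.** 2 + 2 + 2 + 2 = 8. Two are restricted by name, so 8 − 2 = 6 are listed without a causality limit. Under the literal rule, each of the two overall tables becomes identical to its related-only counterpart, leaving 8 − 2 = 6 distinct tables. Under the limited reading all 8 are distinct. Only the limited reading fits the list.

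**Which events are affected.** Of the five grades, the lower two (definitely unrelated, unlikely related) fall outside the related class. The upper three and missing relationship stay in under either reading.

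**Size in any one cell.** Let A be the number of subjects with at least one event in that SOC or PT, and R the number with at least one such event graded in the upper three categories or with relationship missing. The literal rule shows R where the table title promises A, a shortfall of A − R. This lies between 0 (every affected subject also has a related event there) and A (none does). In the severity tables, a subject who stays in can also move to a lower grade if the most severe event was one of those removed. The documents give neither A nor R, so no percentage can be attached.

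**Dependence on what is recorded.** Protocol Section 9 has two recording rules that conflict. One records events from the procedure onward if they are in the study eye and judged related to the implant or procedure. The other counts any clinically significant change after treatment, whatever its cause. If sites follow the first, few unrelated events reach the database and the filter has little to remove. If they follow the second, the filter has its full effect.

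**The case against.** The strongest reply is that the section resolves its own slip. The sentence stands in the paragraph on relationship, which ends with a counting rule for subjects with several related events. The severity paragraph opens its counting rule with the same phrase about all tabulations, although counting at maximum severity has meaning only in severity tables. The phrase may therefore mean all tabulations of that attribute. The duplicate tables that follow from a literal reading, the unfiltered protocol 8.5.1 and the declaration of no changes in SAP Section 10 point the same way. SAP Section 1 places the table specifications in another document, which may settle the matter.

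Most of this stands as evidence of intent, but it does not remove the conflict. Counting each subject once can sensibly apply to every table, so the parallel phrase is not conclusive. The specifications were not available for this review. The related-only recording sentence in protocol Section 9 also makes a related-only table look less obviously unintended than it otherwise would.

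A reader might infer that the SAP plans to suppress unrelated events and so make the exchange look safer. The documents do not support that. All adverse events remain in the by-subject listing, serious events and deaths have their own listing, and missing relationship and missing severity are both resolved conservatively.

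**Conclusion.** The contradiction is real, and the sentence is wrong as written. Its stated scope cannot be reconciled with six of the eight tables and the overview in the same section, or with protocol 8.5.1. The narrow scope was probably intended, so this is a rule to correct, not evidence that unrelated events will be dropped.

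If the rule were applied literally, the loss would be confined to counts and percentages in the tabulations; the listings would stay complete. The size cannot be estimated, because it depends on the unknown mix of causality grades and on which recording rule the sites follow. The conclusion rests on the SAP text alone and assumes that no unseen specification already limits the rule.

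**What to change.** Replace the sentence in SAP 7.1.2 with wording such as:

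> For tabulations of TEAEs related to study treatment, events graded possibly, probably or definitely related, or with relationship missing, count as related, and only these are shown. All other TEAE tabulations (overview, SOC/PT, maximum severity, serious) include TEAEs regardless of relationship.

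In the overview, the related-only definition then applies to the treatment-related row alone. Check the separate table specifications against this wording before database lock. The two recording rules in protocol Section 9 also need to be reconciled, since they determine which events the tables can contain.

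The cost is one sentence and a check of the table shells. No new data or analysis is needed, and SAP Section 1 already allows amendment before lock. The counts in the six all-causality tables and the overview will be equal to or higher than under the literal rule.
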